10.6.3 Pre-Discharge Follow-Up Visit

Prior to being discharged from the hospital, subjects will complete a pre-discharge visit. The evaluation while in the hospital will include but is not limited to the following:

- Complete Physical Exam to assess for procedure related complications per investigational center's standard of care including but not limited to:
 - a. Vital signs (blood pressure, heart rate, respiration rate, temperature) will be obtained.
 - b. Cardiovascular and pulmonary examination.
 - c. Standard neurological assessment.
 - d. Assessment of catheter insertion sites (both sides of the groin).
- Assess the subject for any adverse events following ablation procedure.
- Perform a 12-lead ECG.
 - a. Report presence or absence of Atrial Fibrillation or other supraventricular tachycardias
- NIH Stroke Scale Evaluation follow-up.
- Provide subjects with cardiac event monitor and operating instructions.
- Record medication changes since ablation procedure.
 - a. Cardiac, AAD, diuretic, or anticoagulation.

Subjects will be discharged from the hospital when stable, per the Investigator's discretion.

10.7 Scheduled Follow-up Visits

10.7.1 Seven Day Follow-up Phone Call

All subjects must be evaluated seven days (7 ± 3 days) post ablation procedure. The follow-up will be conducted over the phone and the following evaluation will be completed:

- Adverse Event Assessment.
 - Ask the subject if there have experienced any new adverse events since discharge from the hospital and inquire about resolution of any previously reported event(s).
- Medication changes
 - Ask subject if there have been any changes in their regularly prescribed medications (cardiac, AAD, diuretic, or anticoagulation).
 - Review event monitor data for recordings made due to symptomatic episodes of arrhythmias since the last follow-up.

10.7.2 One Month Follow-Up Visit

All subjects must be evaluated at one month (30 ± 14 days) after the index ablation procedure. During the follow up, the following will be performed:

- Perform a complete physical exam with vital signs and 12-lead ECG.
 - Cardiovascular and pulmonary examination.
 - Standard neurological assessment.
 - Assessment of catheter insertion sites (both sides of the groin).
- Administer a follow-up NIH Stroke Scale assessment.
- Assess the subject for any new adverse events and inquire about resolution of any previously reported events(s).
- Record any medication changes.
- Review event monitor data for recordings made due to symptomatic episodes of arrhythmias since the last follow-up.

- If there has been an early recurrence of AF, Investigator should schedule a visit so he/she can evaluate subject to determine if a repeat ablation procedure can be scheduled before the end of the 90-day blanking period.

10.7.3 Repeat Ablation Procedure (if applicable)

It is expected that some subjects will have early recurrences of atrial arrhythmias (e.g. AF, AT, AFL) within the blanking period (~90 days following the ablation procedure). ^[19] Investigators may perform repeat ablation procedure in subjects with highly symptomatic or multiple early recurrences of atrial arrhythmias that cannot be controlled with antiarrhythmic therapy. ^{[10] [20]} Subjects with documented early recurrence during the blanking period are not being considered a primary effectiveness failure.

The repeat ablation procedure during the blanking period must be performed with the investigational catheter. Prior to the repeat ablation procedure, subjects must meet the pre-ablation requirements described in this protocol. Investigators must follow all procedural requirements defined in this protocol for the repeat ablation procedure. During the repeat procedure, the presence or absence of PV electrical reconnection will be recorded. In addition, the location of reconnection will be noted.

The blanking period and follow-up visit schedule will not restart following the repeat ablation procedure. Subjects that receive a repeat ablation procedure will undergo a repeat ablation pre-discharge visit. Each Repeat Ablation Procedure and discharge will be documented in a CRF. Adverse Events for recurrent AF are not required to be collected for Repeat Ablation Procedures.

Commercial devices are allowed for use during a Repeat Ablation Procedure that is performed after the Blanking Period (~90 days post index ablation procedure), and will also be documented in a CRF.

10.7.4 Three Month Follow-Up Visit

All subjects must be evaluated three-months (90 ± 21 days) following the index ablation procedure.

During this follow-up visit, the following will be performed:

- Perform a limited physical exam (weight, resting heart rate, and blood pressure).
- Assess the subject for any new adverse events and inquire about resolution of any previously reported events(s).
 - Subjects who have experienced symptoms or adverse events suggestive of PV stenosis are required to receive a chest CT or MRI scan to rule out PV stenosis.
- Perform a 12-lead ECG.
 - Report the absence or presence of Atrial Fibrillation or other atrial tachyarrhythmia.
- Record any medication changes.
- Review event monitor data for recordings made due to symptomatic episodes of arrhythmias (if applicable).
- Instruct subject to record twice-monthly 1-minute recordings as well as symptomatic events.
- Subjects will be instructed on how to use the event monitor to capture 24-hour Holter reading and the data will be transmitted remotely to the Corelab.

10.7.5 Six Month Follow-Up Visit

All subjects must be evaluated six-months (180 ± 28 days) following the index ablation procedure.

During this follow-up visit, the following will be performed:

- Perform a limited physical exam (weight, resting heart rate, and blood pressure).
- Assess the subject for any new adverse events and inquire about resolution of any previously reported events(s).
 - Subjects who have experienced symptoms or adverse events suggestive of PV stenosis are required to receive a chest CT or MRI scan to rule out PV stenosis.
 - Perform a 12-lead ECG.
 - Report the absence or presence of Atrial Fibrillation or other atrial tachyarrhythmia.
- Record any medication changes.
- Review event monitor data for recordings made due to symptomatic episodes of arrhythmias (if applicable) since the last follow-up and the event monitor data from the two (2) required monthly recordings.
- Subjects will be instructed on how to use the event monitor to capture 24-hour Holter reading and the data will be transmitted remotely to the Corelab.
- Administer a follow-up AFEQT Questionnaire (QOL).

10.7.6 Twelve Month Follow-Up Visit

All subjects must be evaluated twelve-months (365 ± 45 days) following the index ablation procedure.

During this follow-up visit, the following will be performed:

- Perform a limited physical exam (weight, resting heart rate, and blood pressure).
- Assess the subject for any new adverse events and inquire about resolution of any previously reported events(s).
 - Subjects who have experienced symptoms or adverse events suggestive of PV stenosis are required to receive a chest CT or MRI scan to rule out PV stenosis.
 - Perform a 12-lead ECG.
 - Report the absence or presence of Atrial Fibrillation or other atrial tachyarrhythmia.
- Record any medication changes.
- Review event monitor data for recordings made due to symptomatic episodes of arrhythmias (if applicable) since the last follow-up and the event monitor data from the two (2) required monthly recordings.
- Subjects will be instructed on how to use the event monitor to capture 24-hour Holter reading and the data will be transmitted remotely to the Corelab.
- Administer a follow-up QOL assessment (AFEQT Questionnaire).
- Administer a follow-up NIH Stroke Scale assessment.

10.7.7 Alternative Methods for Follow-Up Visits

Alternative methods of data collection may be necessary in the case of extenuating circumstances, such as a global pandemic, when subjects are prohibited from coming into the office for required assessments. These are listed below as “alternative processes used only during extenuating circumstances”. Data unable to be collected remotely or via an alternative method should be collected at the next possible in-person visit.

In the event a subject is unable to return for an in-office follow-up visit, the alternative methods of obtaining follow-up assessments include virtual visit and/or phone visit. The study assessments which may not be feasible to be completed via the alternative methods are listed below:

1. Virtual Visit, i.e. inclusive of video with study subject.

The following assessments may not be (fully) completed with a virtual visit:

- Physical examination (limited review per physician discretion).
- Chest CT or MRI scan to rule out PV stenosis*:
 - Make every effort to schedule in-person imaging as soon as possible.
 - When possible, the subjects could be referred to a local imaging center for assessment.
Local imaging technicians would require study training and delegation prior to assessment.
- NIH Stroke Scale assessment (limited review per physician discretion).

2. Phone Visit, i.e. no video with the subject.

The following assessments may not be (fully) completed with a phone visit:

- Physical examination (limited review per physician discretion).
- Chest CT or MRI scan to rule out PV stenosis*:
 - Make every effort to schedule in-person imaging as soon as possible.
 - When possible, the subjects could be referred to a local imaging center for assessment.
Local imaging technicians would require study training and delegation prior to assessment.
- NIH Stroke Scale assessment.

* Subjects who have experienced symptoms or adverse events suggestive of PV stenosis are required to receive a chest CT or MRI scan to rule out PV stenosis.

10.7.8 Unscheduled Visits

Unscheduled visits may occur at any time during the study for the assessment of for example, possible adverse events and/or medication changes. Each unscheduled visit will be documented in a CRF.

10.8 Protocol Deviations

Under emergency circumstances, deviations from the Clinical Investigation Plan to protect the rights, safety and well-being of human subjects may proceed without prior approval of the Sponsor and the IRB/EC. The use of waivers for deviating from the Clinical Investigation Plan is prohibited, going forward the study will be executed under Medtronic procedures.

Reports of any deviation from the Clinical Investigational Plan as per above emergency circumstances will be reported to the Sponsor and to the IRB/EC as soon as possible after detection, but no later than twenty-four (24) hours from the time of the deviation.

Deviations must be documented on the appropriate protocol deviation CRF.

Any report of withdrawal of IRB/EC approval will be submitted to the Sponsor within five (5) working days.

If a Clinical Monitor or Medtronic Representative becomes aware that an Investigator is not complying with the signed Investigator's Agreement, the Clinical Investigational Plan, the requirements of ISO14155:2020 or other applicable regulations, or any conditions of approval imposed by the reviewing IRB/EC Committee, the Sponsor will immediately either secure compliance or discontinue shipments of the device to the Investigator and terminate the Investigator's participation in the investigation. The Investigator will be required to return all investigational components to the Sponsor, unless this action would jeopardize the rights, safety or welfare of a subject.

Protocol deviations will be analyzed by the Sponsor for the impact to the overall integrity of the study. Input from the statistician and/or the Data Safety Monitoring Board (DSMB) may be obtained to determine if the deviation warrants disqualifying the Investigator.

Disqualification is warranted when an Investigator has repeatedly or deliberately violated governing regulations or has repeatedly or deliberately submitted false information in any report. Where protocol deviations occur, which do not warrant disqualification from a study, the Sponsor will implement appropriate corrective and preventive actions, including repeat training as deemed necessary.

10.9 Subject Exit, Withdrawal or Discontinuation

All subjects enrolled in the clinical study (including those withdrawn from the clinical study or lost to follow-up) will be accounted for and documented. If a subject withdraws from the clinical study, the reason(s) will be documented. Reasons for withdrawal may include physician discretion, subject choice to withdraw consent, lost to follow-up or death, etc. While study withdrawal is discouraged, subjects may withdraw from the study at any time, with or without reason, and without prejudice to further treatment.

All applicable case report forms up to the point of subject withdrawal must be completed. For subjects who are "lost-to-follow-up" the Investigator/center should have at least three documented attempts to contact the subject prior to withdrawal from the study. No additional data may be collected after a subject has been withdrawn from the study or withdraws his/her consent, for whatever reason. At the time of study exit, all adverse events with an outcome of ongoing must be reviewed by the Investigator to determine a final status of the event. Data collected up to the point of subject withdrawal may be used.

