10.11 Subject Lost to Follow-Up

The Investigator will attempt to contact a subject at least three times prior to designating them as lost-to-follow-up subjects; two of these attempts should include attempting to contact subject via registered mail. The Investigator will document the date and type of attempted communication and will complete

the Study Completion Form when a subject is lost to follow-up. When subjects are lost to follow-up the Investigator will make efforts to confirm the vital status of the subject. If allowed per local regulations, a person identified by the subject is informed of the possibility to be contacted by the principal investigator regarding how to reach the subject and the subject's health status and a civil register may be contacted by the principal investigator to inquire about the subject's whereabouts.

11. Risks and Benefits

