12.4 Reporting of Adverse Events

Reporting of AEs to the Sponsor will occur on an AE CRF, including AE description, AE start date, seriousness, treatment, relatedness to the device and procedure and AE outcome. Each AE must be recorded on a separate AE CRF.

Planned hospitalization for a pre-existing condition, or a procedure required by the Clinical Investigational Plan, without serious deterioration in health, is not considered as part of the primary composite safety endpoint. Additionally, underlying diseases/ pre-existing conditions will not be reported as an AE unless there has been a substantial increase in the severity or frequency of the problem which has not been attributed to natural history during the investigation. To this extent, hospitalizations due to recurrent AF/AT/AFL or prolonged hospitalization following procedure to adjust anticoagulation regimen or to administer diuretic medication are not considered AEs for this study. Adverse Events for recurrent AF are not required to be collected for Repeat Ablation Procedures.

For any changes in status of a previously reported adverse event (i.e. change in treatment, outcome, relatedness), an update to the original AE must be provided. All AEs must be followed until the AE has resolved, the subject exits the study or until study closure, whichever occurs first.

In the event that a subject is exited from the study prior to study closure, all efforts should be made to continue following the subject until all “ongoing” procedure or device related AEs are resolved.

At the time of study exit, all AEs with an outcome of “ongoing” must be reviewed and updates provided as applicable.

Upon Sponsor receipt of an AE, a Sponsor representative will review the AE for completeness and accuracy and when necessary will request clarification and/or additional information from the Investigator. The Sponsor will utilize MedDRA, the Medical Dictionary for Regulatory Activities, to assign a MedDRA term for each AE based on the information provided by the Investigator.

For emergency contact regarding a UADE, USADE, SAE and/or SADE, contact a study representative immediately (refer to the study contact list provided in the study site's study documents binder/Investigator site file or refer to the Sponsor contact information provided on the title page).

Adverse Events will be classified according to the standard definitions in Table 13 and the responsibilities outlined below in Table 12:

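### The protocol bars all data after any withdrawal yet asks sites to keep following ongoing related adverse events, so post-exit safety outcomes can go unrecorded

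*Protocol*

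**What the plan says.** Four provisions of the protocol and one of the SAP bear on this.

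- **Protocol 10.9, the ban:** "No additional data may be collected after a subject has been withdrawn from the study or withdraws his/her consent, for whatever reason". The same section says: "Reasons for withdrawal may include physician discretion, subject choice to withdraw consent, lost to follow-up or death, etc". It keeps the case report forms up to the point of withdrawal and requires that, at exit, "all adverse events with an outcome of ongoing must be reviewed by the Investigator to determine a final status of the event".
- **Protocol 12.4, general rule:** "All AEs must be followed until the AE has resolved, the subject exits the study or until study closure, whichever occurs first".
- **Protocol 12.4, next paragraph:** "In the event that a subject is exited from the study prior to study closure", then "all efforts should be made to continue following the subject until all “ongoing” procedure or device related AEs are resolved".
- **Protocol 10.11:** "When subjects are lost to follow-up the Investigator will make efforts to confirm the vital status of the subject".
- **SAP 7.4:** subjects who leave early without a primary failure are censored at last study contact in the Kaplan-Meier analysis. A tipping-point analysis then imputes them as failures one by one, in order of censoring time, until the confidence bound crosses the performance goal.

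The primary safety endpoint (Protocol 14.4.1, SAP 7.9.1) counts most components within 7 days, significant pericardial effusion within 30 days, and pulmonary vein stenosis and atrioesophageal fistula through 6 months.

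**The concern.** A subject withdrawn early with an ongoing related adverse event falls under two instructions that cannot both be followed. The ban in 10.9 is not confined to withdrawal of consent, the one case where it is clearly needed. It also covers subjects whom the physician withdraws and subjects who are lost. With up to 30 sites, practice may differ from one site to the next.

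Two things are at stake. The first is the outcome of adverse events already under way at exit, including any whose duration decides whether they count toward the primary safety endpoint. The second follows from the breadth of 10.9 alone: the two harms tracked to 6 months cannot be recorded if they begin after an early exit. Censoring at last contact treats leaving as unrelated to harm. If subjects who are doing badly leave more often, the event rate is understated.

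**Working it through.** **Step 1. Apply the rules to three example subjects.** The examples are constructed; the criteria are those of Protocol Table 6.

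| Subject | 10.9 | 12.4 or 10.11 | Result |
|---|---|---|---|
| A. Related pericarditis starts on day 3; physician withdraws the subject on day 20 with it ongoing | No data after day 20; a final status is set at exit | 12.4 general rule: follow-up ends at exit. 12.4 next paragraph: make all efforts to follow to resolution | Direct conflict. If no other pericarditis criterion is met, persistence beyond 30 days decides whether the event counts, and this cannot be known on day 20 |
| B. Lost to follow-up in month 4 | Counts as withdrawn; no further data | 10.11: try to confirm vital status | Tension. 10.9 places three contact attempts before withdrawal, so the vital-status check can be read as preceding the cut-off |
| C. Withdrawn in month 2 with nothing ongoing; pulmonary vein stenosis or fistula begins in month 4 | Cannot be recorded | 12.4 covers only events already ongoing at exit | Not captured under either rule; the loss comes from the breadth of 10.9 |

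Subjects who exit after completing 12 months raise no conflict.

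**Step 2. How many early exits does the plan expect?** Neither document gives a count. From the sample-size sections (Protocol 14.7, SAP 6), drop-out is 12% and the larger required size is 274.

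- 274 / (1 − 0.12) = 311.4, taken as 311. The safety size gives 269 / 0.88 = 305.7, or 306.
- 0.12 × 311 = 37.3, so about 37 early exits.
- The share leaving before day 180 is not stated. As an assumption, one quarter, one half or three quarters of 37 gives about 9, 18 or 28 subjects with a shortened 6-month window.

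**Step 3. How close is the safety test to its limit?** SAP 7.9.1 uses a log-log bound. With complete follow-up (a simplification) and x events among n subjects:

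- S = 1 − x/n, with Greenwood variance S(1 − S)/n
- se = √(S(1 − S)/n) / |S log S|
- upper bound on the event rate = 1 − S^exp(1.96 × se), to be below 11.5%

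| n | events | rate | se | upper bound | result |
|---|---|---|---|---|---|
| 311 | 24 | 7.72% | 0.204 | 11.29% | pass |
| 311 | 25 | 8.04% | 0.200 | 11.66% | fail |
| 269 | 20 | 7.43% | 0.224 | 11.29% | pass |
| 269 | 21 | 7.81% | 0.218 | 11.72% | fail |

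At the planned 7% rate, the expected count is 0.07 × 311 = 21.8 against a limit of 24, or 0.07 × 269 = 18.8 against a limit of 20. The margin is about one to two events. The drop-out count of 37 belongs with the n = 311 rows.

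**The case against.** The strongest reply has five parts.

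- **The conflict is narrow.** The paragraph after the general rule in 12.4 can be read as a special provision for early exits, and it asks for best effort without imposing a firm duty. The vital-status request in 10.11 may precede formal withdrawal. This stands in part: one clear conflict remains, between 10.9 and 12.4, for subjects withdrawn early with an ongoing related event.
- **Late fistula and stenosis are not lost through that conflict.** This stands. A reader might infer that settling the conflict in favour of 12.4 would recover them. It would not, because 12.4 is limited to events already ongoing.
- **Events before exit are kept.** This stands. A reader might infer, for instance, that phrenic nerve paralysis in a subject withdrawn in month 2 drops out of the endpoint. Table 6 requires only persistence beyond 7 days, so it has already qualified; the 12-month permanence label feeds no stated objective.
- **The tipping-point analysis covers harm-related exit.** It shows how many imputed failures would reverse the conclusion, and that is a real safeguard. It recovers no outcomes, and the SAP does not say what tipping count would be acceptable.
- **Few events are likely to be missed.** If the late-event risk were 0.1% to 1% (an assumption), 18 shortened windows would hide about 0.02 to 0.18 events in expectation. The documents give no rate that would confirm or refute this.

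**Conclusion.** The contradiction between 10.9 and 12.4 is real and unreconciled, and 10.11 is in tension with 10.9. Following 10.9 loses the later course of ongoing related adverse events, which can reach the primary safety endpoint where a component depends on duration. Separately, because the ban extends beyond withdrawal of consent, stenosis or fistula that begins after exit but within 6 months goes unrecorded.

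The size is bounded only loosely: about 37 early exits of about 311, an unknown share of them before day 180, and a pass limit of 24 events under complete follow-up. The number of events actually missed cannot be derived.

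A reader might infer that one unrecorded event would overturn the safety result, or that the bias demonstrably favours the device. The documents support neither. One event always decides a threshold test at its boundary, which says nothing about how many are missed. That exits are related to harm is plausible, but no figure in the plan shows it.

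**What to change.** Reconcile Protocol 10.9, 10.11 and 12.4, and align SAP 7.4:

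1. In 10.9, limit the ban to subjects who withdraw consent to further data collection.
2. For other early exits, permit follow-up of ongoing procedure- or device-related adverse events. Where consent allows, also permit collection of vital status and the 6-month safety endpoint status by phone or record review.
3. In 12.4, make the sentence that ends follow-up at exit consistent with the paragraph after it.
4. In SAP 7.4, count these contacts when setting the safety censoring date, and keep the tipping-point analysis for subjects who remain unobserved.

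The cost is a protocol amendment with the approvals at each site that section 15.1 requires, possibly new consent wording, and a limited number of calls or record checks. No new visits or tests are needed. The change helps only where consent permits, and data on subjects already withdrawn may not be recoverable.
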